4.2 Key Secondary Objective(s) & Endpoint(s)

Secondary objectives

- To evaluate the efficacy of TOFA with SLE-CL over time compared to baseline

Secondary endpoint

Part A and B:

- Proportion of subjects that achieve a skin response (complete or partial response) as per the validated (CLASI) at weeks 4, 8 and 24 compared to baseline at TD1¹⁴. Response is defined as follows:
 - *Complete response (CR)* : complete resolution of the inflammatory rash (CLASI activity score = 0);
 - *Partial response (PR)*: $\geq 20\%$ improvement of the CLASI activity score. A partial response (PR) is considered clinically significant
 - *No response*: $< 20\%$ improvement or even worsening of the CLASI activity score
 - *Cutaneous relapse*: a new CLASI activity score ≥ 4 in those subjects who previously achieved CR of SLE-CL (CLASI=0)

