4.3 Exploratory Objective(s) & Endpoint(s)

Exploratory objectives

Part A:

- To evaluate single cell expression patterns of skin biopsies of affected and non-affected skin with TOFA therapy
- To examine changes in interferon α/γ receptor, STAT phosphorylation patterns with TOFA therapy using immunohistochemistry
- To investigate mRNA expression patterns in peripheral blood upon treatment with TOFA with focus on interferon regulated genes

Parts B and C:

- To evaluate steroid sparing properties of TOFA for SLE-CL
- To evaluate TOFA effect of overall disease activity in SLE as measured by the SLEDAI and BILAG
- To evaluate effects of TOFA on quality of life as measured by the Skindex (appendix 4) and overall well-being

Exploratory endpoints at week 4, 8, 12, 24, 52, and 76

Part A: Pharmacodynamics (PD)

- PD parameters include assessment of inhibitory effect of TOFA on expression of IL-2 responsive target genes downstream of the JAK/STAT pathway, such as FOXP3, SOCS3, IL-2R α , interferon - γ and granzyme B.

Parts B and C:

- Decrease of absolute dose of systemic CS from baseline
- Decrease of body weight adjusted CS dose from baseline
 - CS dosing is measured in prednisone-equivalents
- Proportion of subjects who discontinue systemic CS
- Proportion of subjects with cutaneous relapse
- Change of BILAG score from baseline¹³
- Absolute value and percent change in plasma: Complement C3 and C4d, autoantibodies (anti-dsDNA)
- Change in number of inflamed joints from baseline¹⁴
- Change in SKINDEX score from baseline¹⁵
- Change of CLASI damage score¹⁶ from baseline
- Change in SLEDAI score at each time point
- Change in protein: creatinine ratio at each time point.
- Change in subject's overall well-being at each time point
- Change in subject's ESR
- Proportion of subjects with clinically important reduction in SLE activity at each time point, based on CRV changes compared to baseline
- Proportion of subjects with flare of SLE activity at each time point, as defined by the BILAG¹⁷

Data of subjects who enter Part B before week 8 and/or Part C before week 24 will be considered on a last-observation (LOC) carried forward basis for endpoints of Part A and B, respectively.

5. Study Participants

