5.1 Inclusion Criteria

1. Male or female ≥ 18 years of age and ≤ 45 years of age and > 40 kg body weight.
2. Fulfilled at least 4 out of the 11 Classification Criteria for SLE by the time of screening¹⁸.
3. Willing to give written informed consent, must fully understand the requirements of the trial, and must be willing to comply with all trial visits and assessments.
4. CLASI activity score of 8 or higher¹⁹ at screening and baseline despite standard of care therapy.
5. Stable dose of prednisone of ≤ 20 mg/day within 2 weeks of enrollment.

6. Female subjects of childbearing potential must use a highly effective method of contraception to prevent pregnancy (abstinence is considered highly effective) and must agree to continue to practice adequate contraception for the duration of their participation in the trial and for 28 days after their last dose of TOFA.
7. Female subjects of childbearing potential must have a negative serum pregnancy test at screening and a negative urine pregnancy test at Trial Day 1 before dosing.
8. For subjects receiving leflunomide treatment, total daily dose does not exceed 20 mg.
9. A negative QuantiFERON-TB Gold In-Tube test performed within the 3 months prior to screening, or within the screening period prior to baseline. A negative PPD test can be substituted for the QuantiFERON-TB.
10. Subjects either have protective varicella titers or evidence of having been vaccinated against varicella.

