6.2 Dosing

TOFA dosing: Twice daily orally

As documented in the TOFA Investigator brochure (Section 6.1; Version March 2016) doses up to 30 mg twice daily were safe and tolerated. However, for the purpose of this study only the dose of TOFA approved for rheumatoid arthritis (5 mg PO BID) will be tested.

Based on TOFA PK in the Rheumatoid Arthritis (RA) population [body weight (BW) ranging from 40 kg - 140 kg)], clearance (CL) of TOFA is not dependent on body weight in adult subjects. Thus, the starting dose of TOFA will be 5 mg orally twice daily, an approved dose of TOFA in adult RA subjects in most countries. Dose escalation will not occur even with lack of SLE-CL improvement.

Corticosteroids (CS):

At study entry, CS dosage must be \leq 20mg/day. CS should be kept stable up to and including week 4.

CS can be decreased starting week 5:

- CS may be decreased for improvement of the CLASI activity score by \geq 50% from baseline and must be tapered for CLASI activity scores of 0 for $>$ 8 weeks (or 2 subsequent study visits, whatever is shorter), provided CS are mainly prescribed for SLE-CL. This will minimize morbidity associated with CS use as much as possible.
- If CS are mainly prescribed for other SLE manifestations besides SLE-CL, then CS can be decreased as per the investigator's decision, even in the setting of complete response of SLE-CL, based on continued improvement of clinical findings of SLE.

Oral CS may be increased above the baseline level up to max of 60 mg/day for new BILAG A or B flares in organ systems other than mucocutaneous organ system (i.e. neurologic, ophthalmologic, musculoskeletal, cardiopulmonary, gastrointestinal, renal, hematological organ systems) but must be returned to baseline dose or lower within 14 days. If this is not achieved then the subject is considered a treatment failure.

- Up to 3 doses of pulse methylprednisolone may be given for new BILAG A or B flares instead.
- CS increases can occur no more than 3 times during the duration of the study, Part A- C.
- Subjects requiring more than 3 CS increases will be withdrawn from treatment phase of study.

Other anti-inflammatory medications used as part of standard of care (SOC) for SLE

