6.5 Rescue clause, treatment failure & subject withdrawal

A subject will be considered a treatment failure and discontinued from the study if he/she experiences one or more of the following:

- Serious adverse event that is possibly related to TOFA;
- Important worsening of renal disease defined as a persistent increase in proteinuria as measured by the protein: creatinine (PC) ratio to values > 2.0 after achieving complete response of lupus nephritis, or doubling of proteinuria with values PC ratio > 3.0 after achieving a partial response of lupus nephritis;
- Need to increase current or initiation of new SLE background therapy due to non-renal SLE manifestations;
- Life-threatening SLE complications as judged by the investigator;
- Need for more than the protocol defined allowable CS rescue therapy as determined by the treating physician;
- No improvement of SLE-CL as measured by the CLASI by week 8;
- Two sequential absolute lymphocyte counts less than $< 0.5 \times 10^9$ or 500 cells/mm³;
- Two sequential hemoglobin values < 8.0 g/dL (80 g/L) or decreases greater than 2 g/dL on treatment;
- Female subjects that become pregnant during the study will discontinue study treatment. They will be continued to be followed in accordance as outlined in section **7.3.10**.

Subject Withdrawal

Subjects may withdraw from the study at any time at their own/their legal guardian's request, or they may be withdrawn at any time at the discretion of the physician investigators for safety, behavioral, or administrative reasons. If a subject does not return for a scheduled visit, every effort should be made to contact the subject. In any circumstance, every effort should be made to document subject outcome, if possible.

The investigator will inquire about the reason for withdrawal, request the subject to return all unused investigational product, request the subject to return for a final visit, if applicable, and follow-up with the subject regarding any unresolved AEs.

7 If the subject withdraws from the study, and also withdraws consent for disclosure of future information, no further evaluations should be performed, and no additional data should be collected. The sponsor may retain and continue to use any data collected before such withdrawal of consent. Planned Assessments & Evaluations

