8.3 Effectiveness Analyses

Due to the small sample size, results may not show statistical significance. Statistical significance may not be reached in final data analysis. However, a trend towards improved clinical status may assist planning efforts of a larger clinical trial to assess efficacy.

The efficacy population will be all subjects who were enrolled in the study and received at least 1 dose of TOFA. No interim analyses are planned. We will perform intention-to-treat analyses, with the last observation carried forward in primary analyses; and will also perform analyses on observed data in secondary analyses. As this is an open-label study, no control group is available. Efficacy measures are listed under Section 7. Data of subjects who enter Part B before week 8 and/or Part C before week 24 will be

considered on a last-observation (LOC) carried forward basis for endpoints of Part A and B, respectively.

To assess the benefits of TOFA on skin manifestations of SLE, we will use descriptive analysis and contingency table analysis, using Chi-square and Fisher Exact test as appropriate, to determine the proportion of subjects who are partial or complete CLASI responders at weeks 4, 8 and 24 compared to baseline. To assess the effect of TOFA on skin damage, we will compare the change (increase) of CLASI damage score¹⁶ from baseline to the end of Part B and C, respectively, using paired T-tests.

To assess the steroid –sparing properties of TOFA, we will determine the proportion of study subjects who can discontinue steroids at the end of Part B and C, respectively. We will also evaluate steroid sparing properties of TOFA for SLE-CL by comparing steroid doses (absolute and weight-adjusted) at baseline with those in the end of Part B and C, using a paired T-test.

Similarly, we will assess TOFA effect of overall disease activity in SLE as measured by the numeric SLEDAI and BILAG scores, respectively. We will also perform sub-analyses and evaluate improvement or resolution of other organ-system activity (e.g. serological activity – measured by anti-dsDNA antibodies and low complement levels; joint counts) using paired T-tests and contingency table analysis, as appropriate. In a similar fashion the change of the other SLE core response variables (CRV) besides disease activity (SLEDAI, BILAG) will be assessed at each study visit.

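### Under the planned LOCF, a subject discontinued as a treatment failure can count as a week-24 CLASI responder, and no planned rate counts that subject as a failure

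*Combined protocol and SAP*

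**What the plan says.** **Analysis rule.** Section 8.3 takes everyone enrolled and dosed as the efficacy population and says: "We will perform intention-to-treat analyses, with the last observation carried forward in primary analyses". Observed-data analyses are secondary. Sections 4.3 and 8.3 add that data of subjects who enter Part B or Part C early are "considered on a last-observation (LOC) carried forward basis for endpoints of Part A and B, respectively".

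**Endpoint.** Section 4.2 makes CLASI response (complete or partial) at weeks 4, 8 and 24 a secondary endpoint. Complete response is an activity score of 0, partial response is at least 20% improvement, and anything less is no response. It adds: "A partial response (PR) is considered clinically significant". Treatment status plays no part. Entry requires a "CLASI activity score of 8 or higher" (section 5.1).

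**Failure and stopping.** Section 6.5 opens its list with: "A subject will be considered a treatment failure and discontinued from the study if he/she experiences one or more of the following". Among the items are a possibly related SAE, worsening proteinuria, low lymphocytes or hemoglobin, pregnancy, and "Need to increase current or initiation of new SLE background therapy due to non-renal SLE manifestations". On corticosteroid increases not brought back down within 14 days, section 6.2 says: "If this is not achieved then the subject is considered a treatment failure". Serious infection (section 7.3.4) and liver injury (section 7.3.6) also force a stop.

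**After stopping.** Section 7.1 schedules one safety phone call 10 weeks after the last dose. On withdrawal, section 6.5 has the investigator "request the subject to return for a final visit, if applicable".

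Sections 4.2 and 8 and Appendix 3 section J do not say how a treatment failure enters the response rate.

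**The concern.** The protocol uses two classifications that never meet. One is clinical: a subject is a treatment failure and leaves. The other is numerical: the last CLASI is compared with baseline. When a subject leaves for a reason other than skin while the rash is still improved, LOCF carries the improved score to week 24 and reports a response.

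The observed-data analysis does not supply the missing view, because it removes the subject from the denominator. A reader of both planned rates would not see how many of the 20 both responded and avoided failure.

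What is at stake is modest but specific. With no control arm, the response proportion is the main skin-efficacy figure the study passes on, and section 8.3 says its trend may help to plan a larger trial. A planner could take the LOCF figure as the share still responding on treatment at week 24, which it is not.

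**Working it through.** The plan states no expected response rate, discontinuation rate or power, and Appendix 3 section D says no formal sample size estimation was done. There is no planned figure to reproduce, so the check traces the rule and then counts.

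**1. How small a fall is a response?** The minimum whole-point fall is 20% of baseline, rounded up.
- Baseline 8: 1.6, so 2 points (25%)
- Baseline 9: 1.8, so 2 points (22%)
- Baseline 10: 2.0, so 2 points (20%)
- Baseline 11: 2.2, so 3 points

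Near the entry minimum, a 2-point fall at the last visit is enough.

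**2. How old can the carried value be?** Section 7.1 puts visits at weeks 10, 12, 16, 20 and 24 in Part B. If the last CLASI comes from week 8, 10, 12, 16 or 20, it is 16, 14, 12, 8 or 4 weeks old at week 24. A CLASI taken at a final visit would be fresher, but it is still a value from the time of stopping. For the week-4 and week-8 rates visits are roughly weekly, so the gap is at most a few weeks.

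**3. Gap between counting rules.** Let N = 20 dosed, r = responders observed at week 24, k = subjects discontinued for failure or a mandatory safety stop with last CLASI improved by at least 20%, and m = others removed without response.
- LOCF: (r + k)/N
- Failures as non-response: r/N
- Observed data: r/(N − k − m)

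LOCF minus failures-as-non-response = k/N = k/20. For k = 1, 2, 3, 4 this is 5, 10, 15, 20 percentage points. The sign follows from the definitions.

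**4. Illustration** (assumed, not from the documents: r = 10, k = 2; exact Clopper-Pearson 95% intervals).

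| Rule | Count | Rate | 95% CI |
|---|---|---|---|
| LOCF | 12/20 | 60% | 36–81% |
| Failures as non-response | 10/20 | 50% | 27–73% |
| Observed, m = 0 | 10/18 | 56% | 31–79% |
| Observed, m = 3 | 10/15 | 67% | 38–88% |
| Observed, m = 6 | 10/12 | 83% | 52–98% |

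The observed-data rate can fall on either side of LOCF, depending on m. It cannot fall below r/N, because only its denominator shrinks. The intervals overlap widely.

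**5. Roll-over sentence.** Part C can begin at week 8 for a subject in skin remission and off corticosteroids (section 4.1 footnote). Read literally, a subject who enters then with CLASI 0 and stops at week 12 for a related SAE is a complete responder at week 24. This is a constructed case. It shows only that the sentence can produce the same result by a second route.

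**The case against.** **The endpoint is a skin response.** Someone whose rash improved and who stopped for low lymphocytes or pregnancy did have one. Safety is already a primary endpoint, reported in all dosed subjects, so building failure into the skin rate counts tolerability twice. This stands as a question of estimand, and it is why LOCF should be kept. But the plan does not say that its rate means last observed skin status.

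**The upward direction is built in.** A reader might infer that LOCF overstates the true week-24 response. The documents do not support that: skin status after stopping is not scheduled to be measured, so the gap compares two counting rules.

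**Not every failure is affected.** A subject removed at week 8 for no CLASI improvement, or whose last score has already lost response, is a non-responder under LOCF too. Added therapy and excess corticosteroid rescue can also be driven by the skin.

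**Some who meet a criterion may stay.** A reader might infer that everyone who meets a failure criterion should be a non-responder. That goes too far. The section 6.2 sentence on corticosteroids does not itself say the subject is discontinued. Section 3 lets therapies other than tofacitinib be altered in Part C, while section 6.5 makes some such changes a failure. These passages need reconciling. Meanwhile such a subject may have a genuine week-24 CLASI, which a counting rule should not overwrite.

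**Staleness may be less than shown.** A final visit is requested where applicable, and the schedule has an end-of-study column. If CLASI is done then, the ages in step 2 are upper limits.

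**Conclusion.** The point holds as a gap in the counting rules. As written, a subject discontinued before week 24 for a protocol-defined failure or a mandatory safety stop, with a last CLASI at least 20% better than baseline, is a week-24 responder under LOCF and absent from the observed-data rate.

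Each such subject separates LOCF from a failure-as-non-response rate by 1/20, or 5 points, assuming all 20 planned subjects are dosed (1/N otherwise). That step is exact. The number of such subjects is unknown and may be zero, and the 60% against 50% example rests on assumed counts.

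A reader might infer that LOCF must be replaced or that the efficacy conclusion is unsound. Neither follows: the endpoint is secondary and uncontrolled, it has no success threshold, section 8.3 claims only a trend, and a skin-only rate is a legitimate quantity once labelled. The change is worth making because it is cheap and adds a rate that a planner needs and the plan does not report.

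**What to change.** In section 8.3, for CLASI response (chiefly week 24, with the same rule at weeks 4 and 8):

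- Pre-specify an analysis with all dosed subjects in the denominator. A subject actually discontinued before the visit for a section 6.2 or 6.5 failure or withdrawal criterion, or for a mandatory safety stop (serious infection, liver injury), and with no CLASI at that visit, is a non-responder.
- Do not overwrite a CLASI observed at the visit. Leave other missing values under LOCF, such as missed visits, personal or administrative withdrawal, or a stop under section 6.4.
- Report this rate beside the LOCF rate with equal prominence, with the number of subjects whose status changes. Label LOCF as last observed skin status.
- State that the roll-over carry-forward sentence does not override the rule for a subject who rolls over early and later stops.

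**Cost.** SAP wording and one derived flag; CLASI and reasons for discontinuation are already collected. The added rate is 5 points below LOCF per affected subject. It is a composite of skin response and absence of failure, and must be described as such: a real skin responder stopped for safety or pregnancy counts as a non-responder in it, while the LOCF rate beside it still shows the response. No treatment, stopping or rescue rule changes.

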This 76-week, 3-part, Phase 1b/2 study is intended to evaluate the pharmacological properties (pharmacokinetics and pharmacodynamics) of TOFA administrated to young adults with moderately to severely active inflammatory *SLE-CL*.

- **Part A** (up to week 8) requires stable background medications;
- **Part B** (up to week 24) allows for tapering of *corticosteroids (CS)*, *in the setting of significant clinical improvement of SLE-CL as defined by a decrease in Cutaneous Lupus Erythematosus Disease Area and Severity Index (CLASI) activity score by ≥50% from baseline*, and

Part C (until week 76) permits tapering of other background medications in subjects with clinical remission of SLE-CL (CLASI activity score=0). TOFA dosing is kept stable during Part C.

Primary Objective

Part A (Cohort 1):

- To evaluate the pharmacokinetic (PK) profiles of TOFA in young adults aged between 18 and including 45 years with SLE -CL who are on stable treatment for SLE

Part A (Cohort 1 and Cohort 2)

- To evaluate the safety and tolerability of TOFA in young adults with SLE -CL

Part B and C:

- To evaluate the safety and tolerability of TOFA in young adults with SLE -CL

Primary endpoints

Part A (Cohort 1 only):

- **Day 5:** AUC_{inf} and C_{max} of tofacitinib

Part B: At Week 24

- Nature, severity, and frequency of adverse events
- Incidence and severity of laboratory abnormalities

Key Secondary Objective(s) & Endpoint(s)

Secondary objectives

- To evaluate the efficacy of TOFA in young adults with SLE -CL

Secondary endpoint**Part A and B****Efficacy on SLE skin disease**

- Proportion of subjects who achieve a skin response (complete or partial response) as per the validated Cutaneous Lupus Erythematosus Disease Area and Severity Index (CLASI) at weeks 4, 8 and 24 compared to baseline¹⁶. Response (compared to baseline at TD1) is defined as follows:
 - *Complete response (CR)* : complete resolution of the inflammatory rash (CLASI activity score = 0);
 - *Partial response (PR)*: $\geq 20\%$ improvement of the CLASI activity score
 - *No response*: $< 20\%$ improvement or even worsening of the CLASI activity score (CLASI relapse)

Exploratory Objective(s) & Endpoint(s)**Exploratory objectives****Part A:**

- To evaluate single cell expression patterns of skin biopsies of affected and non-affected skin with TOFA therapy
- To examine changes in interferon α/γ receptor, STAT phosphorylation patterns with TOFA therapy using immunohistochemistry

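### The planned chi-square/Fisher test of CLASI responders against baseline has a comparator that is zero by definition and made up of the same subjects

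*Combined protocol and SAP*

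**What the plan says.** Section 8.3 sets out how the skin benefit of tofacitinib will be assessed: descriptive analysis plus "contingency table analysis, using Chi-square and Fisher Exact test as appropriate, to determine the proportion of subjects who are partial or complete CLASI responders". The full target of the analysis is "partial or complete CLASI responders at weeks 4, 8 and 24 compared to baseline". The same section states that "As this is an open-label study, no control group is available", warns that "Statistical significance may not be reached in final data analysis", and hopes that "a trend towards improved clinical status may assist planning efforts of a larger clinical trial to assess efficacy".

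Section 4.2 makes skin response the secondary endpoint. Complete response (CR) is a CLASI activity score of 0. Partial response (PR) is an improvement of at least 20% in that score, and the section adds: "A partial response (PR) is considered clinically significant". Both are judged against the subject's own TD1 score; Appendix 3, part B, repeats this: "Response (compared to baseline at TD1) is defined as follows". Section 5.1 requires a "CLASI activity score of 8 or higher" at both screening and baseline.

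Appendix 3, part J, says that categorical outcomes will be reported as frequencies or rates and numeric outcomes analysed with paired t-tests. Neither document part plans a confidence interval for the responder proportion, and neither gives an alpha level or a reference response rate.

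**The concern.** A contingency-table test needs two groups. The only comparator named is baseline, and at baseline nobody can be a responder. There are two separate faults:

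- **Structural zero.** The null hypothesis is in effect that the response rate is zero. Rejecting it says nothing about response beyond what would be seen without the drug.
- **Pairing.** Chi-square and Fisher tests assume independent groups, but both rows hold the same subjects. Section 8.3 uses paired t-tests for its other baseline comparisons, so pairing was recognised there but not here.

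The stakes are interpretive. A small p-value on the secondary efficacy endpoint, with PR labelled clinically significant, could be read as evidence of benefit and carried into the design of a larger trial. What that design needs is a response rate with its uncertainty.

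**Working it through.** **Inputs from the documents.** n=20, in two cohorts of 10 on the same dose (Section 3). CR and PR definitions (Section 4.2). Baseline activity score at least 8 (Section 5.1). Cohort 2 opens only if at least one Cohort 1 subject has a PR by week 4 (Section 3).

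**Assumptions.** Alpha is taken as two-sided 0.05. The rate of at least 20% CLASI improvement without the drug is taken as 10%, 20% or 30%. The documents give neither, and there is no planned power figure to reproduce, because Appendix 3, part D, says that no formal sample size estimate was made.

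**Step 1: the baseline row.** At TD1 the change from TD1 is 0%, which is below 20%, so no subject is a PR. The score is at least 8, so no subject is a CR. The row is 0/n with certainty.

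**Step 2: p-values for r/n against 0/n.** The two-sided Fisher p is 2 × C(n,r)/C(2n,r). The exact McNemar p, with r discordant pairs all in one direction, is 2 × 0.5^r.

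| n | r | Fisher p | McNemar p |
|---|---|---|---|
| 20 | 4 | 2 × 4845/91390 = 0.106 | 0.125 |
| 20 | 5 | 2 × 15504/658008 = 0.047 | 0.0625 |
| 20 | 6 | 0.020 | 0.031 |
| 10 | 4 | 2 × 210/4845 = 0.087 | 0.125 |
| 10 | 5 | 2 × 252/15504 = 0.033 | 0.0625 |

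At 5 responders, ignoring the pairing is enough to move the result across 0.05. The uncorrected chi-square statistic is 2nr/(2n−r). At 4/20 that is 160/36 = 4.44, p=0.035, where Fisher gives 0.106. The expected responder count there is only 2 per row, so a usual small-count rule would choose Fisher, but Section 8.3 states no rule.

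**Step 3: chance of Fisher significance with no drug effect.** P(X ≥ 5) at one time point, X binomial:

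| Assumed no-drug rate | n=20 | n=10 |
|---|---|---|
| 10% | 0.043 | 0.002 |
| 20% | 0.370 | 0.033 |
| 30% | 0.762 | 0.150 |

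These figures ignore the Cohort 2 gate. If Cohort 2 stays closed because no Cohort 1 subject responded, the week-4 count is 0, so the n=10 column could apply only at weeks 8 and 24. If Cohort 2 opens, an early response rate of zero has already been disproved before the test is run.

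**Step 4: is zero a plausible no-drug rate?** At the minimum entry score, 20% of 8 is 1.6. CLASI activity is a sum of whole-number items (Appendix 5), so a 2-point fall counts as PR. Natural fluctuation and rater variation of that size cannot be excluded.

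**Step 5: what an interval would show.** The Clopper-Pearson 95% limits are the 0.025 quantile of Beta(x, n−x+1) and the 0.975 quantile of Beta(x+1, n−x). For 5/20 = 25% they are 8.7% to 49.1%; for 5/10 = 50% they are 18.7% to 81.3%.

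**The case against.** The strongest reply is that the table of r/n against 0/n is not what the authors meant. In Section 4.2 the reference to baseline defines response, and Section 8.3 may only be repeating that. This is a fair reading, but it does not rescue the test: with one arm and no grouping factor named for this endpoint, there is nothing to cross-tabulate. The fault then changes from an invalid comparison to one that cannot be carried out.

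Second, other parts of the plan soften the problem. Descriptive results are promised, and the paired t-tests in Appendix 3, part J, arguably cover the numeric CLASI activity score listed in Section 7.1.1. That stands, and the response proportions themselves are unaffected. But it supplies neither a comparator nor an interval for the responder endpoint.

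Third, the consequences are limited. No primary endpoint, cohort gate or decision rule uses this p-value, and Section 8.3 already concedes the lack of a control and that significance may be missed. This stands and caps the severity. The caveat warns of a negative result, however, not that a positive one would be uninterpretable.

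Fourth, the probabilities in Step 3 rest on assumed rates, and the Fisher/McNemar difference crosses 0.05 only at exactly 5 responders. Both are true. Section 6.5 and Appendix 3, part H, also discontinue subjects without improvement or response by week 8, and the last observation is then carried forward. A simple binomial count is therefore a rough description of week 24. The figures illustrate scale and are not forecasts.

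**Conclusion.** The concern holds. On one reading, the stated test is an independent-groups comparison of paired data against a structural zero; on the other, it has no second group. In neither case does it inform the question of benefit.

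The practical size depends on quantities the documents do not give. With a two-sided 0.05 level and 20 subjects, the chance of a significant Fisher result at one time point without any drug effect runs from 4% to 76% as the no-drug rate goes from 10% to 30%. With 10 subjects it runs from 0.2% to 15%. The problem is therefore anywhere from negligible to large. It touches the interpretation of a secondary endpoint and the planning of a later trial, not the conduct of this one. It should be fixed, but it does not threaten the primary objectives.

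**What to change.** In Section 8.3, delete the chi-square/Fisher comparison with baseline and substitute wording such as:

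> The proportions of treated subjects with CR, PR and CR+PR at weeks 4, 8 and 24 will be reported with exact (Clopper-Pearson) 95% confidence intervals. Without a control group, these estimates do not isolate a drug effect.

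If a comparison between subgroups was intended, name the subgroups. If a test is kept, make it a one-sample exact binomial test against a justified benchmark, with alpha and sidedness fixed before database lock. As an illustration, at an assumed one-sided 0.025, the smallest k with P(X ≥ k) ≤ 0.025 is:

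| Benchmark | n=20 | n=10 |
|---|---|---|
| 10% | 6 (0.011) | 4 (0.013) |
| 20% | 9 (0.010) | 6 (0.006) |
| 30% | 11 (0.017) | 7 (0.011) |

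The cost is a small wording amendment to a protocol that the IRB reviews (Appendix 3, part G), with no new data or visits. The sponsor gives up a p-value that could not be interpreted. Keeping a test would mean justifying a benchmark rate, which the documents do not supply.
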